**Tracking dietary changes:** We will utilize the Food Frequency Questionnaire (FFQ) originally developed by Drs. Gladys Block and Linda Harlan, often referred to as the "Block FFQ" . This questionnaire collects information about eating habits over a 12-month period. The FFQ contains approximately 105 items grouped by categories and is completed for both frequency of consumption as well as portion size selections by the individual. The questionnaire, upon completion, provides estimated daily intake values for selected nutrients (kilocalories, macronutrients, and micronutrients) and provides information on food group servings. **All participants will be instructed and reminded regularly not to alter dietary habits or engage in purposeful dieting during the intervention.**

**Blood sample collection:** Trained personnel will obtain fasting venous blood samples from the antecubital site with participants in a seated position. Either 21 or 23 gauge needles will be used, depending on vascular access. Standard OSHA guidelines will be followed at all times. At baseline and follow-up, a total of 20 mL of blood will be drawn. Of this, 10 mL will be immediately sent to the Clinical Laboratory for lipid assessment, insulin and blood chemistries. Lipids and other biochemical measures will be made using standard analytic techniques. The remaining 10 mL sample will be centrifuged under refrigerated conditions, and the supernatant will be extracted, and divided into 1 mL portions. Vials of plasma (3-4), serum (2-3), and red blood cells (2-3) will be stored at -80°C for future analysis.

**3.6 Recruitment and Pre-Screening:** Study personnel will screen interested individuals over the phone based on the inclusion/exclusion criteria. Eligible individuals will be invited to attend an **orientation session**, during which study personnel will provide a presentation with detailed information about the study (structure of the study, study-related procedures, risks, benefits, etc.). Individuals interested in I-CAN following this orientation session will be consented at this time, and scheduled for run-in visits.

**Run-in visits:** The run-in period will last for two weeks in order to: 1) verify sedentary status (pedometry) and screen for other inclusion/exclusion criteria (e.g. BMI, waist circumference, blood pressure); and 2) ensure participants are able to make the time commitment to come to

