**Figure 4. Web-based questions to determine pedometers compliance.**

**Pedometer compliance tracking:** We will utilize RED Cap™, a secure online research database to: 1) track and monitor participant compliance wearing pedometers; and 2) record Non-Ex PA at run-in and during the intervention. Participants will be provided a unique name/password to log on to the study website. The use of RED Cap™ will allow our staff to monitor participant compliance throughout the trial in real-time. Our research team is successfully using RED Cap™ in two on-going prospective physical activity trials.

**3.7 Clinical Visits (baseline, mid-intervention, and follow-up):** We will obtain primary (waist circumference) and secondary outcome measures (DEXA, fitness, blood measures) at both baseline and follow-up (summarized in Figure 5). Pre-menopausal women will be asked to take a pregnancy test. A physician or a physician’s assistant will obtain a medical history and perform a brief medical exam. **All clinic staff measuring outcome measures will blinded to participant randomization.**

At mid-intervention (week 12), we will measure waist circumference, weight, FFQ, and accelerometry. The CON group will be scheduled for mid-intervention and follow-up visits, and will be instructed not to alter physical activity habits during the intervention. All groups will be instructed not to alter dietary habits during the study.

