**3.11 Statistical Considerations:** The results of the present pilot trial will be used to inform the design (effect size/statistical power) of a larger prospective intervention (to be developed into a future R01 application). Baseline participant characteristics (e.g., age sex, race, weight, BMI, waist circumference, % body fat, fat mass, lean mass, cholesterol, triglycerides, blood pressures) will be summarized by group (CON, AERO, and AERO-PA) as counts and percentages for categorical variables, and means and 95% confidence intervals or medians and IQRs for continuous variables. Adherence to protocol assessments (e.g., daily steps, minutes spent in very low activity, aerobic sessions/week, percent of peak VO2, MET levels) will be summarized similarly by week for each intervention. On study change in peak VO2, estimated METs, weight, waist circumference, cholesterol, triglycerides, and blood pressures will be summarized in an intention-to-treat analysis of (1) all participants and (2) the subset of participants who achieve a high level of adherence to protocol. Linear models will provide the primary framework for significance testing. Statistical significance of differential longitudinal changes in response to interventions will be assessed employing repeated measures mixed effects models with maximum likelihood estimation and Kenward-Rogers adjustment to the degrees of freedom in an intention-to-treat analysis of (1) and (2) for each outcome using all available data. The two interventions, measurement times (e.g., baseline, mid-intervention, study exit), race, sex and interactions will be taken as fixed effects; participants within groups will be considered as having random effects. Other covariates such as age and baseline assessments will be included in preliminary models and retained in final analytical models if warranted. The model covariance structure (e.g.: unstructured, compound symmetric, auto-regressive) across time will be investigated to enhance efficiency of statistical tests. Results for each outcome will be summarized as least squares means and 95% confidence intervals for each intervention across the assessment times (repeated measures). Model residuals will be tested to see if they have distributions that are approximately Gaussian and data transformations will be performed if needed. Group differences in baseline characteristics will be tested and corrective steps taken, such as post-stratification and adding model covariates as necessary. Linear contrasts on least squares means will be used to test differential mean changes in each outcome from baseline to subsequent assessment times between the two intervention groups. Null hypotheses will be tested against two-directional alternatives at the

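### Whether the change contrast is adjusted for baseline is left to unstated criteria and baseline significance tests; one baseline-adjusted model per outcome should be fixed in advance

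*Combined protocol and SAP*

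**What the plan says.** All the analysis text is in section 3.11 (Statistical Considerations). Intervention and measurement time, with baseline counted as a time, enter a mixed model, and "race, sex and interactions will be taken as fixed effects". The test is a contrast of change: "Linear contrasts on least squares means will be used to test differential mean changes in each outcome from baseline to subsequent assessment times".

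Two further sentences govern adjustment. One concerns retaining covariates: "Other covariates such as age and baseline assessments will be included in preliminary models and retained in final analytical models if warranted". The other concerns imbalance: "Group differences in baseline characteristics will be tested and corrective steps taken, such as post-stratification and adding model covariates as necessary". Neither gives a significance level, a list of variables, a retention criterion or the form in which a covariate enters. No other section fixes a final model for waist circumference or any other outcome.

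The intended use is also stated: "The results of the present pilot trial will be used to inform the design (effect size/statistical power) of a larger prospective intervention".

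The visit schedule bears on the remedy. Section 3.7 has "At mid-intervention (week 12), we will measure waist circumference, weight, FFQ, and accelerometry", but "secondary outcome measures (DEXA, fitness, blood measures) at both baseline and follow-up". Section 3.5 agrees for blood: "At baseline and follow-up, a total of 20 mL of blood will be drawn".

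**The concern.** Under randomisation, a significant baseline difference is a chance event. It does not show whether adjustment will help; that depends on how strongly baseline predicts the outcome, which can be judged beforehand. With 15 per arm the baseline test is also insensitive. The retention sentence might be a sounder rule, but as written it cannot be carried out in only one way.

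Three things are at stake: some precision, protection in a trial whose arms happen to differ at baseline, and a final model that does not depend on the data. The third matters because outcomes are formally tested at two-sided 0.05 and the estimated effect is meant to size the next trial.

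**Working it through.** The plan states no power, SD or correlation, so it has no figure to reproduce.

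**Inputs.** From the documents: three arms of 15 (section 3.2) and two-sided 0.05 (section 3.11). Assumed: SD 10 cm at both visits; baseline-to-week-24 correlation ρ of 0.8 to 0.9 for waist and 0.5 for a noisier outcome; complete data. The contrast is AERO-PA minus AERO at week 24.

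**1. Plain change.** SE = √[2 × 2(1−ρ) × 10² / 15]. At ρ = 0.9 this is √(40/15) = 1.63 cm; at 0.8, √(80/15) = 2.31; at 0.5, √(200/15) = 3.65.

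**2. Planned adjustment.** In large samples the variance ratio to plain change is (1−ρ²)/[2(1−ρ)] = (1+ρ)/2. Estimating one pooled slope on 42 within-group degrees of freedom multiplies this by 1 + 1/40 = 1.025. The ratios are 0.95 × 1.025 = 0.974, 0.90 × 1.025 = 0.922 and 0.75 × 1.025 = 0.769. Simulation agrees.

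**3. Chance gaps.** The SE of the baseline gap between two arms is 10 × √(2/15) = 3.65 cm. A gap larger than this occurs in about 32% of trials, and the three-group test at 0.05 misses about 88% of them. Given a gap d, the plain change contrast is displaced by (1−ρ)d in absolute size. For d = 3.65 cm that is 0.37, 0.73 or 1.83 cm at ρ = 0.9, 0.8 or 0.5.

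**4. What the unstated rule would do.** Null simulations (3 × 15, 100,000 to 200,000 trials per ρ) compared two readings: adjust only if the three-group test of the outcome's own baseline is significant, or keep baseline if its slope has p < 0.05. Both assume an effective form of adjustment (step 5).

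| | ρ 0.9 | ρ 0.8 | ρ 0.5 |
|---|---|---|---|
| SE, plain change (cm) | 1.63 | 2.31 | 3.65 |
| SE, planned adjustment (cm) | 1.61 | 2.22 | 3.20 |
| Share of gain kept, baseline-test trigger | 18% | 18% | 19% |
| Share of gain kept, slope p < 0.05 | 17% | 58% | 96% |
| Null rejected, gap > 1 SE: plain change | 5.9% | 6.7% | 9.0% |
| Same trials: baseline-test trigger | 5.6% | 6.1% | 7.6% |
| Same trials: planned adjustment | 5.0% | 4.9% | 5.0% |
| Null rejected, all trials: plain change | 5.0% | 5.0% | 5.0% |
| All trials: baseline-test trigger | 4.9% | 4.9% | 4.6% |
| All trials: better of adjusted and unadjusted | 6.1% | 6.4% | 7.3% |

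Slope-based retention gives about 5.2 to 5.4% over all trials. When the baseline test is significant (5% of trials), the adjusted and unadjusted waist estimates differ by a median of 0.53 cm (ρ 0.9) or 1.12 cm (ρ 0.8). That is 0.53/1.63 = 0.3 or 1.12/2.31 = 0.5 of an SE.

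**5. The form matters.** A covariate entered only as a main effect beside group-by-time leaves the complete-data change contrast unchanged. In one simulated three-visit data set the contrast was 0.997 with no covariate, with age, or with baseline as a main effect. With baseline-by-time it became −0.603, the ANCOVA value. The plan does not say which form is meant.

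**The case against.** The strongest reply has four parts, and much of it stands.

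- **The default is sound.** An unadjusted difference in change, from a mixed model with baseline as a response, is unbiased and holds 5%. A reader might infer that the plan yields a biased primary result or an inflated error rate. The documents do not support that: neither the default nor a mechanical baseline-test trigger raises overall type I error, and slope-based retention barely does.
- **The retention sentence naturally means keeping a covariate that predicts the outcome.** On that reading most of the gain survives where it is large (96% at ρ 0.5). A reader might infer that the plan forfeits over four-fifths of the available precision. That holds for the imbalance trigger and, at ρ 0.9, for the slope rule too, where there is little to gain. It is not a property of the plan as a whole.
- **For waist the loss is trivial.** An SE of 1.61 rather than 1.63 cm will not change a conclusion, and a 5% test is expected to miss most one-SE gaps. In sizing a later trial, sampling error at 15 per arm dominates. This stands, and it limits the severity.
- **It is a pilot with an acknowledged small sample.** True, but it sets formal tests for each outcome and passes its effect size on.

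Two further inferences should be avoided. The plan does not say that the analyst will pick the more favourable result; it only fails to exclude it. Nor is the place of race and sex open: both are already fixed effects, and only the other covariates are conditional.

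**Conclusion.** The point holds as a pre-specification weakness of minor to moderate severity. Section 3.11 has a valid default contrast but leaves conditioning on baseline to two open-ended sentences, one of which uses a poor trigger.

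Planned adjustment would cut the variance by about 3% to 8% for waist (ρ 0.9 to 0.8) and by about 23% for an outcome with ρ 0.5. It would also hold the error rate near 5% in trials with a chance baseline gap, where plain change gives 5.9% to 9.0%. How much of this the plan would deliver cannot be known from its text. The consequence that follows most directly from having no criterion is room for choice: at worst an overall error of about 6.1% to 7.3%.

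The sizes rest on the assumed SD and correlations. The variance ratios and error rates do not depend on the SD, but the figures in centimetres do. The gap in the wording rests on no assumption.

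**What to change.** Name one baseline-adjusted primary model for each clinic-visit outcome.

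- **Outcomes with a week-12 value (waist, weight, accelerometry):** use baseline, week 12 and week 24 as responses with one baseline mean common to all groups, or post-baseline responses with baseline-by-time.
- **Outcomes measured only at baseline and follow-up (DXA, fitness, blood measures):** use ANCOVA of the follow-up value on baseline.
- **Triggers:** delete baseline significance tests as a reason to add covariates or post-stratify.
- **Covariates:** replace the open retention wording with a short list named in advance and entered with time. Put other covariate sets in sensitivity analyses.

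The cost is SAP wording and a changed model statement, with no new data or visits. The downside is that uninformative covariates cost precision with 45 participants. With q covariates in total, the factor in step 2 becomes about 1 + q/(41−q). At ρ 0.9, baseline alone gives 0.974, but baseline plus one uninformative covariate gives 0.95 × (1 + 2/39) = 0.999, which cancels the waist gain. The list should therefore be short and limited to covariates expected to predict change.

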#### 3.2 Approach:

The target study population of the **I-CAN** study will be sedentary obese men and women (BMI: 30-40 kg/m^2, age 40-65 yrs). We will randomize participants to aerobic training (AERO, N=15), aerobic training and increasing Non-Ex PA (AERO-PA, N=15) group or a non-exercise control group (CON, N=15) for 6 months (24 weeks). Participants in the AERO or AERO PA groups will participate in the same structured aerobic training program 3 times per week in a laboratory setting, and wear pedometers during the entire 6 month intervention (except during structured aerobic training sessions). The AERO-PA group, in addition to aerobic training, will increase Non-Ex PA progressively from 1,000 to 3,000 steps/day above baseline from week 6

[figure not shown]

Figure 3. Swift et al. *American Journal of Preventive Medicine*. 2012. Change in waist circumference in the DREW study stratified by amount of Non-Ex PA in the 4, 8 and 12KKW

to week 24 of the intervention. The CON group will continue their current physical activity habits during the intervention. **The primary outcome measure of I-CAN is the change in waist circumference following the intervention.** Secondary measures include change in fitness, body weight, body composition (fat and lean mass), pedometer determined steps/day of Non-Ex PA during the intervention, accelerometer-determined physical activity, fasting glucose, fasting insulin and homeostatic model of insulin resistance (HOMA-IR).

**3.3 Inclusion/Exclusion Criteria:** The inclusion/exclusion criteria are summarized in Table 1. The goal of the I-CAN study is to recruit adults with moderate to high CVD risk that can safely perform the supervised aerobic training in our facility. In addition, all participants must have sufficient health to increase Non-Ex PA in their daily lives, as this will not be directly supervised by study staff. Therefore, we will recruit sedentary obese men and women (age: 40-65) with elevated waist circumference (women:  $\geq 88$  cm, men:  $\geq 102$  cm), and at least one additional CVD risk factor. Individuals with type 2 diabetes and known cardiovascular disease will be excluded due to the pilot nature of this trial, and the necessity to establish the efficacy of this intervention prior its utilization in a higher risk study population.

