**Measurement of waist circumference:** We will utilize standard operating procedures (SOPs) for assessment measures including waist circumference. Staff are tested and certified annually on the correct measurement technique. Participants will stand in a straight, upright position with the feet together with arms at their side. Waist circumference will be measured at the natural waist (midway between the inferior border of the rib cage and the superior aspect of the iliac crest) with a Gulick tape measure. Both landmarks (the inferior border of the ribcage and the superior aspect of the iliac crest) will be marked and the distance will be measured to determine the appropriate measurement site. Staff will confirm that: 1) the measurement tape remains horizontal; 2) the tape touches the entire circumference of the participant; 3) abdominal tissue is not compressed; 3) the tape measure is not within abdominal folds; 4) the measurement is taken at the end of normal respiration. The measurement will be repeated an additional time, and the reported value will be the average of these measurements. Both measurements must be within 0.5 cm to be considered acceptable for data purposes. A third measurement is required if values are > 0.5 cm. Waist circumference will be evaluated at baseline, mid-intervention, and at follow-up.

**3.5 Secondary measures:** Secondary measures include: change in fitness, body weight, body composition, pedometer determined Non-Ex PA during the intervention, accelerometer determined physical activity levels, fasting glucose, fasting insulin and HOMA-IR.

**Anthropometric & Dual Energy X-ray Absorptiometry (DXA):** Height will be measured at screening. Body weight will be evaluated using a calibrated scale (recorded to the nearest 1/10 of a kg), with the participant fasted and wearing only a hospital gown. DXA will be used to measure body composition (fat and lean mass).

**Accelerometry:** At each major assessment point, participants will wear the GT3X+ accelerometer (ActiGraph, LLC, Pensacola, Florida, USA) at their waist for seven consecutive days, 24-hrs/day. We have successfully used this 24-hour protocol in adults and find that it maximizes wear time. This accelerometer has been validated and is one of the most widely used accelerometers in research and has the capability of detecting minute-by-minute

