
nominal 0.05 significance level using Bonferroni adjusted p-values when appropriate. All statistical analyses will be performed using statistical software in SAS version 9.3.

**3.12 Limitations and Strengths:** A limitation of the project is the small sample size. However, we feel this is appropriate due to the pilot nature of the trial. In addition, the results of I-CAN will be used to determine the effect size and to power a larger randomized trial (as an R01 application) with more cardiovascular/diabetes-related outcomes. Another limitation is that we are not measuring total energy expenditure through doubly labeled water (DLW). Due to the high cost of DLW (each participant: \$750, total study costs [baseline and follow-up] = \$67,500), it is not feasible for this pilot project. However, we will incorporate DLW measurements when this study is developed into a larger randomized trial. The strengths of I-CAN are that it is a practical physical activity intervention, the core principles of which (i.e. aerobic training and attainment of high Non-Ex PA) are feasible in clinical, exercise training and public health settings. We have designed our aerobic training intervention to be consistent with public health recommendations. I-CAN will be the first training study to our knowledge with such a strong focus on the measurement of Non-Ex PA (adherence and tracking plan, pedometers [blind mode capable], and the use of internet databases to monitoring Non-Ex PA and support behavior modification) throughout the entire exercise intervention. Results of this pilot project, and the subsequent large randomized controlled trial could have implications for future public health recommendations, and other populations with co-morbid low physical activity and obesity (e.g. adults with cardiovascular disease or type 2 diabetes).

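### Section 3.11 leaves the covariance structure of the primary waist model to an open search for test efficiency; if compound symmetry is used and correlation falls with time, the week-24 test exceeds its 5% level

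*Combined protocol and SAP*

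**What the plan says.** Section 3.2 fixes the primary outcome: "The primary outcome measure of I-CAN is the change in waist circumference following the intervention". Section 3.4 gives three measurement times: "Waist circumference will be evaluated at baseline, mid-intervention, and at follow-up". Section 3.7 puts the middle one at week 12 of a 24-week intervention, so the visits are about equally spaced. Section 3.2 allocates 15 participants to each of three groups.

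Section 3.11 analyses each outcome with a repeated measures mixed model, fitted by maximum likelihood with Kenward-Roger degrees of freedom. Linear contrasts test the difference between groups in change from baseline to each later visit. The tests are two-sided at the "nominal 0.05 significance level using Bonferroni adjusted p-values when appropriate". On the within-participant covariance it says: "The model covariance structure (e.g.: unstructured, compound symmetric, auto-regressive) across time will be investigated to enhance efficiency of statistical tests". On random effects it says that "participants within groups will be considered as having random effects".

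The three structures are given only as examples. No criterion for choosing among them, no default, no fallback order and no robust variance is stated.

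**The concern.** The covariance structure sets the standard error of the primary contrast. Compound symmetry assumes one correlation for all pairs of visits, so it assigns one common variance to the 0-12, 12-24 and 0-24 week changes. When correlation falls as visits lie further apart, the 0-24 change is the most variable of the three, and the pooled figure is too small for it. The confidence interval is then too narrow and the p-value too small.

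Two features of the plan make this a practical risk. A random participant intercept alone implies compound symmetry, so that structure is a natural starting point. And the only stated purpose of the search is test efficiency, which gives the analyst no protection against settling on a structure whose apparent efficiency comes from being wrong. Kenward-Roger corrects for small samples within the assumed structure; it does not detect or correct a wrong one.

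**Working it through.** **Inputs from the documents.** Three groups of 15 (45 in all), three visits, two-sided 0.05, contrast of change from baseline between two groups.

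**Assumed, because the documents are silent.** The waist correlations, equal variances across visits, complete data, and no race, sex or other covariates.

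**Formula.** Write ρ13 for the correlation between baseline and week 24, and ρ̄ for the mean of the three pairwise correlations.
- True variance of the 0-24 change: 2σ²(1 − ρ13).
- Variance used under compound symmetry: 2σ²(1 − ρ̄).
- Ratio: R = (1 − ρ13)/(1 − ρ̄).
- Error degrees of freedom under compound symmetry: 2 × (45 − 3) = 84, critical t = 1.989.
- Actual type I error: 2·P(t84 > 1.989/√R).

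**The plan's own figure.** With constant correlation, R = 1 and the formula returns 0.050, the stated level.

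**One case in full.** First-order autoregressive decay with adjacent correlation 0.90 gives ρ13 = 0.81 and ρ̄ = (0.90 + 0.90 + 0.81)/3 = 0.87. Then R = 0.19/0.13 = 1.462. The standard error is 1/√1.462 = 0.83 of what it should be, about 17% too small. The effective cut-off is 1.989/1.209 = 1.645, and the type I error is 0.104.

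| Adjacent / 0-24 correlation | ρ̄ | R | Type I error, week 24 |
|---|---|---|---|
| constant | – | 1.000 | 5.0% |
| 0.95 / 0.94 | 0.9467 | 1.125 | 6.4% |
| 0.95 / 0.93 | 0.9433 | 1.235 | 7.7% |
| 0.95 / 0.92 | 0.9400 | 1.333 | 8.9% |
| 0.90 / 0.81 (autoregressive) | 0.8700 | 1.462 | 10.4% |
| 0.95 / 0.9025 (autoregressive) | 0.9342 | 1.481 | 10.6% |
| 0.95 / 0.87 (steeper) | 0.9233 | 1.696 | about 13% |

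**The week-12 contrast moves the other way.** At autoregressive 0.90, the ratio is (1 − 0.90)/(1 − 0.87) = 0.769. The cut-off becomes 1.989/0.877 = 2.267 and the type I error about 2.6%.

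**Simulation check.** 8,000 null trials per scenario, 15 per group, three groups, same assumptions.
- Autoregressive 0.90: compound symmetry rejects in 10.3% (REML) and 10.9% (ML) of trials; unstructured in 5.1% and 5.4%.
- Keeping the smallest p-value of the three structures in that scenario: 10.3-10.9%, the same as compound symmetry alone.
- AIC or BIC choice: 5.3-5.7% in that scenario, because compound symmetry is then picked in only about 4-5% of trials. At 0.90/0.85 they pick it in 34-40% of trials, and overall error is 4.9-6.7%.
- Unstructured specified in advance, across all the patterns tried: 4.7-5.4% with REML, 5.4-6.2% with ML.

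**Why ML runs high.** ML divides by 45 where REML divides by 42, so the variance shrinks by 42/45 = 0.933. The unstructured cut-off falls from 2.018 (42 degrees of freedom) to 2.018 × √0.933 = 1.950, and 2·P(t42 > 1.950) = 0.058, inside the simulated range.

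**The case against.** The strongest reply is that modelling the covariance well and parsimoniously is the ordinary route to efficient tests, and that the sentence means no more than that. This has force. A reader might infer that the team will keep whichever structure gives the smallest standard error or p-value; section 3.11 does not say so. Under a sensible fit criterion the error is about 5-7%, close to nominal. What stands is that the plan states no criterion, so whether the primary test holds its level depends on a rule the reader cannot see.

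A reader might also infer that type I error roughly doubles whenever correlation falls with time. That is too general. It takes autoregressive-like or steeper decay; mild decay gives about 6-9%. With no waist correlations in the documents, even the presence of decay is an assumption. Nor is the error always toward false positives: the week-12 contrast becomes conservative, and fitting an autoregressive structure when correlation is truly constant gives about 1% at week 24, a loss of power.

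A third tempting inference is that a random participant effect beside an unstructured residual would invalidate the contrast. The plan does not say the two will be fitted together. If they were, the random effect would be redundant and might hinder convergence, but the marginal covariance would still be unstructured and the contrast would not be biased.

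Finally, this is a 45-person pilot meant to supply an effect size. With balanced, complete data the choice of structure leaves the estimate unchanged. That limits the consequence. But section 3.11 still plans significance tests and 95% confidence intervals, and the pilot is also meant to judge efficacy.

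**Conclusion.** The concern holds in a conditional form. The plan leaves the covariance of its primary model to a data-based search with test efficiency as its only stated aim and no rule for the choice. If compound symmetry is the result and correlation falls with time, the nominal 5% test of the week-24 waist contrast runs at about 6-9% under mild decay, 10-11% under autoregressive decay at 0.90-0.95, and about 13% at 0.95/0.87; with constant correlation it is correct.

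These figures rest on assumed correlations, equal variances, complete data and no covariates. The damage is to standard errors, confidence intervals and p-values, not to the complete-data estimate. An unstructured covariance with REML holds the level near 5% for every pattern examined, so the exposure is avoidable at little cost.

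**What to change.** In section 3.11:

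- Pre-specify an unstructured within-participant covariance for the primary analysis. Three visits need only 6 parameters.
- Omit a separate random participant effect, which is redundant beside an unstructured residual.
- Fit by REML with Kenward-Roger in place of the stated maximum likelihood. With 15 per group, ML variance costs about half a point to one point of type I error (5.4-6.2% against about 5%).
- Name one fixed fallback structure, used only if the model does not converge, with a robust variance.
- Delete the search over structures and the closing phrase about test efficiency.

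The cost is wording. The statistical price, if compound symmetry were in fact true, is error degrees of freedom of about 42 instead of 84 (complete data, before race, sex and other terms). That moves the critical t only from about 1.99 to 2.02.
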